3.0 Study Endpoints/Events/Outcomes

- 3.1 Primary Endpoint/Event/Outcome: Caregiver self-efficacy and competence
- 3.2 Secondary Endpoint(s)/Event(s)/Outcome(s): Caregiver distress (subjective stress and depressive symptoms), negative health transitions for person with ADRD (falls, wandering), service utilization of person with ADRD (residential care placement, hospitalization).

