1.0 Objectives

Purpose: Sensor-based technologies that operate remotely and are non-invasive could assist family caregivers monitor the daily function of persons with Alzheimer's disease or a related dementia (ADRD). The eNeighbor technology platform includes a combination of remote sensors that are located in key areas of a person with ADRD's home (e.g., bed, medicine cabinet or refrigerator doors, toilet, living rooms). Such sensors can immediately communicate any function that is outside of an expected threshold for the person with ADRD to both a family caregiver and a care professional (e.g., nurse care manager). The goal of the remote health monitoring technology such as eNeighbor is to prevent negative health transitions such as falls or wandering events, and thus provides a more proactive intervention model than many clinical protocols that are currently delivered to family caregivers of persons with ADRD. The Lutheran Home Association, a non-profit long-term care provider located in Belle Plaine, Minnesota, has deployed eNeighbor in residential and home settings the past 5 years.

The objective of this 5-year demonstration project is to build on the work of The Lutheran Home Association and conduct an embedded experimental mixed methods evaluation to determine the efficacy of the eNeighbor technology in improving outcomes among persons with ADRD living in the community and their family caregivers.

In collaboration with a 15-member Community Advisory Board that includes community care providers, healthcare organizations, and ADRD caregivers themselves, the proposed 5-year project will build on the current efforts of TLHA to evaluate eNeighbor remote monitoring technology for persons with ADRD living in the community and their family caregivers. We anticipate that the successful completion of the project aims will position the eNeighbor as an innovative, stakeholder-centric service that offers robust support for family caregivers of persons with ADRD in the community.

The Specific Aims are as follows:

1) To determine the efficacy of remote sensor technology over an 18-month period for 100 persons with ADRD and their caregivers randomly assigned to an eNeighbor treatment condition when compared to 100 usual care controls. We hypothesize:

Hx. 1) Significant ($p < .05$) improvements in caregiver self-efficacy and sense of competence in managing a relative's ADRD;

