analytic design of the study.⁶⁸ In this framework, the researcher identifies the Type I error rate (e.g., $p < .05$) to differentiate between a null and alternative test hypothesis, a suitable level of statistical power (.80 is considered an excellent power value), and the expected difference between the two study groups in order to determine the number of ADRD caregivers to enroll into the project. We sought a sample size that would be sufficient to detect a group difference of 0.50 standard deviation units. This is considered to be a “medium” effect size⁶⁹ and is a reasonable benchmark to evaluate the efficacy of a new behavioral intervention in comparison to an attention control condition. Using these specifications, a sample size of 200 ADRD caregivers (factoring in the anticipated 20% attrition rate) was found sufficient. As noted in various recommendations for mixed methods sampling, 30 participants is considered an adequate sample size for semi-structured interview protocols to ensure the richness and depth of open-ended data collected.^{70,71}

17.3 Statistical Analysis:

Analysis of Specific Aim1: Tests of Hypotheses 1-3.

Data available at baseline, 6 months, 12 months, and 18 months will allow for individual growth curve models that examine change in ADRD caregiver outcomes.^{72,73} Multilevel analysis approaches are available that support growth curve modeling. In this context, growth curve modeling is an example of a 2-stage modeling process consisting of 1) a within-subjects model across time; and 2) a between-subjects model that incorporates caregiver and person with ADRD covariates.^{74,75} The primary independent variable in the proposed investigation consists of an indicator variable for random assignment into the eNeighbor treatment condition or the attention care control. IBM SPSS Statistics 21⁷⁶ will be used to conduct these analyses, as it supports multilevel and growth curve modeling procedures. [name], the PI, has extensive experience conducting longitudinal and growth curve analyses in his prior research on ADRD caregiving.^{46,80,81,88}

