Our proposed analyses will provide in-depth tests of Hypotheses 1 and 2 and partially test Hypothesis 3 (i.e., rates of change in ADRD caregivers’ self-efficacy, competence, subjective stress, depressive symptoms, and frequency of negative health transitions and service use). In one set of outcome evaluations, the baseline value will be included as a covariate, and time will be “centered” at 6-months post-baseline. This scales the intercept effect to be a main effect of eNeighbor group assignment and allows the eNeighbor treatment and the attention control groups to have different 6-, 12-, and 18-month change trajectories, or an expanded eNeighbor treatment*time interaction effect. After establishing that the individual growth parameter estimates have significant variance around the mean trajectories of change in key dependent variables, an eNeighbor treatment vs. attention care control group indicator will be added as the key independent variable to predict intercepts and rates of change in outcomes. Additional analyses will determine if covariates (e.g., stress process model covariates including context of care indicators, primary objective stressors, and resources) significantly vary across the eNeighbor treatment and attention control groups at baseline and over time via growth curve modeling procedures. If statistically significant variations between the eNeighbor treatment and

PROTOCOL TITLE: A Proactive Health Monitoring Intervention for Dementia Caregivers: The eNeighbor

control groups are found, initial status and rate of change parameters for these covariates will be included in all tests to provide additional statistical control.

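### The plan has two primary constructs and two treatment parameters each, but no rule on which result decides Hypothesis 1. If any single win counts, the false-claim rate is about 8% to 18%, not 5%

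*Combined protocol and SAP*

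**What the plan says.** Section 3.1 gives the primary endpoint as "Primary Endpoint/Event/Outcome: Caregiver self-efficacy and competence", with no instrument, visit or success rule. Hypothesis 1 in section 1.0 reads "Significant ($p < .05$) improvements in caregiver self-efficacy and sense of competence in managing a relative's ADRD", so one threshold is set for a pair of constructs.

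Section 17.2 describes a generic calculation in which "the researcher identifies the Type I error rate (e.g., $p < .05$) to differentiate between a null and alternative test hypothesis", with "a suitable level of statistical power (.80 is considered an excellent power value". The target is a single effect: "We sought a sample size that would be sufficient to detect a group difference of 0.50 standard deviation units". That effect is not tied to an intercept, a slope or a visit. The planned number is 200 caregivers, allowing for 20% attrition.

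Section 17.3 summarises the tests of Hypotheses 1 and 2 in terms of rates of change. It also says "In one set of outcome evaluations, the baseline value will be included as a covariate", with time centred at 6 months so that the intercept carries the treatment main effect and the treatment-by-time term carries the difference in trajectory. Once the growth parameters are shown to vary, the treatment indicator is added "to predict intercepts and rates of change in outcomes". Sections 17.1 to 17.3 contain no multiplicity adjustment, no testing order and no statement of which parameter decides.

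**The concern.** Two constructs with two treatment parameters each make up to four tests that bear on Hypothesis 1. A significant 6-month intercept or a significant slope, on self-efficacy or on competence, could be reported as support for it, and nothing in the plan would rule that out. The .05 in Hypothesis 1 would then be the error rate of one test and not of the claim. The trial sets out to determine efficacy, so the error rate of its primary claim should be known before arm comparisons are seen.

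**Working it through.** **Inputs from the documents.** Two primary constructs (3.1); p < .05, undivided (1.0); intercept and rate of change both tested (17.3); 0.50 SD, power .80, 200 enrolled, 20% attrition (17.2); 100 per arm (1.0). Completers: 200 × 0.8 = 160, or 80 per arm.

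**Assumptions, because the documents give no figure.** Two-sided tests, each at .05; construct correlation r_c = 0.3 to 0.7, with 0.9 as an extreme; intercept-slope correlation 0 to -0.7. Under a linear model on the 6-, 12- and 18-month visits, within-person correlations of 0.3 to 0.7 imply about -0.4 to -0.7.

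**Step 1: the plan's own figure.** n per arm = 2(1.960 + 0.842)² / 0.50² = 62.8, so 63. The total is 126, and 126 / 0.8 = 157.5, so 158. The stated 200 is not reproduced exactly, but it is called only sufficient, and it is. With 80 per arm the noncentrality is 0.50 × √(80/2) = 3.162, and t-based power at .05 is 88.2%.

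**Step 2: false-claim rate if any single win counts and neither construct responds.** With independent tests the rate is 1 - 0.95² = 9.75% for two and 1 - 0.95⁴ = 18.5% for four. With correlated tests it is P(any |Z| > 1.96) under a multivariate normal, by simulation:

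| r_c | Either of two constructs | Any of four tests (intercept-slope correlation 0 to -0.7) |
|---|---|---|
| 0.3 | 9.5% | 18.1% to 15.6% |
| 0.5 | 9.1% | 17.3% to 14.9% |
| 0.7 | 8.4% | 16.0% to 13.7% |
| 0.9 | 7.0% | 13.6% to 11.6% |

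**Step 3: false-claim rate if both constructs must succeed.** If neither responds and each has one contrast, the rate is 0.5% to 1.7% for r_c from 0.3 to 0.7. If intercept or slope may count for each, it is 1.1% to 3.5% over that range, and about 5% to 6% at r_c = 0.9. If one construct truly responds and its success is taken as near certain, a false joint claim needs only the other construct to win on intercept or slope. That rate is 9.75% at intercept-slope correlation 0, 9.3% at -0.4 and 8.3% at -0.7.

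**Step 4: what a correction costs.** This takes 0.50 SD as an arm difference at one time point, with 80 per arm and t-based power.

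- Alpha .025 (two constructs, one contrast each): power 81.5%. Required n is 2(2.241 + 0.842)² / 0.25 = 76.04, so 77 per arm, 154 in total, and 154 / 0.8 = 192.5, so 193. This is within 200.
- Both required at .05: joint power 78.4%, 79.8%, 81.0% and 82.6% for r_c = 0, 0.3, 0.5 and 0.7 (normal approximation).
- Alpha .0125 (all four tests kept): power 73.7%. Required n is 90 per arm, 180 in total, and 180 / 0.8 = 225. This exceeds 200.

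**Step 5: if the slope decides.** The documents state no slope effect. Assume 0.50 SD builds up linearly by 18 months, which is 0.50/3 = 0.167 SD per six-month interval. With equal within-person correlation r at the three follow-up visits, SE = √[(2/80)(1 - r)/2]. At r = 0.3, SE = 0.0935, z = 1.78, and power at .05 is Φ(1.78 - 1.96) = 43%. At r = 0.7, SE = 0.0612, z = 2.72, and power is 78%. At .025 the same cases give 32% and 68%. Under an autoregressive correlation, power is lower still.

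**The case against.** The strongest reply is that both Hypothesis 1 and section 3.1 join the constructs with the word and. Read as a requirement on both, the global-null rate is under 5% for construct correlations of 0.3 to 0.7. That reading is fair, and it removes the inflation across constructs. It does not settle intercept against slope, and no section states it as a decision rule.

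Second, section 17.3 gives the parameters different roles: a main effect, an interaction, and a summary of the hypotheses as rates of change. The treatment indicator also enters only after the growth parameters show significant variance, so four tests are not guaranteed. This stands. The any-of-four figure is for the case where all four are run and any one can count. Distinct roles still do not say which parameter decides.

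Three stronger readings are tempting, and the documents do not support them.

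- A reader might infer that every test is run at .05. The threshold appears in Hypothesis 1 and, as an example, in the power text. Section 17.3 sets none for the intercept or the slope.
- A reader might infer a competing primary model without baseline adjustment from the phrase about one set of evaluations. No such model is described, and the phrase may only separate the growth models from the survival models.
- A reader might infer that the plan's false-positive rate simply is 14% to 18%. That needs a rule that any win suffices, and the plan does not state one. Silence permits that use but does not prescribe it.

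**Conclusion.** The point holds in conditional form: the plan leaves open which parameter, and how many constructs, decide its primary hypothesis. If any win counts, the false-claim rate is about 8% to 10% for two constructs and 14% to 18% for four tests. At a construct correlation of 0.9 these become about 7% and 12% to 14%. If both constructs must succeed, the global-null rate is below 5% for correlations of 0.3 to 0.7, but 8% to 10% remains for one construct when the other truly responds. The correlations and two-sidedness are assumptions.

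A reader might also infer that 200 caregivers can absorb any correction. That is shown only for a single-time-point difference of 0.50 SD tested at .025. It fails for a four-way split (about 74%), and under the linear build-up assumption it fails for a slope contrast (32% to 68% at .025 with equal within-person correlation). Nor is the figure of 200 an error: it exceeds the simple requirement, and the hierarchical inputs behind it are not given.

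This should be fixed. The trial remains valid, but the error rate of its primary claim is undefined.

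**What to change.** Before arm comparisons are seen, amend sections 3.1 and 17.3 to do three things.

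1. Name one deciding contrast per construct from the baseline-adjusted growth model: an arm difference at a single visit. Eighteen months is one candidate. The documents do not favour a visit, so the choice is the sponsor's.
2. State the success rule. One option is Holm at overall .05 across self-efficacy and competence, with the smaller p-value compared with .025 and, if that succeeds, the other with .05. The other option is that both must reach .05.
3. Report the remaining intercept and slope tests as supportive.

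The cost is wording and no added participants. Holm brings a stricter first threshold, with about 81% power at .025 in place of 88% at .05. Requiring both constructs gives joint power of about 78% to 83%, slightly under .80 if they are weakly correlated. If the sponsor prefers the slope as the deciding contrast, power must first be recalculated with a stated slope effect and variance components.

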4.0 Study Intervention(s)/Interaction(s)

4.1 Description: The home-based sensor technology of eNeighbor relies on multiple, non-invasive and safe remote monitors that can alert family caregivers and/or health professionals to potentially negative situations that lead to adverse outcomes (e.g., wandering, falls, incomplete activity of daily living tasks). The eNeighbor core system includes four unobtrusive motion sensors that are placed in a living room, bedroom, bathroom, and an entryway that can detect motion in a room to verify daily activity (and do not include a microphone or camera). These motion sensors operate jointly and exchange information to help identify significant changes in movement or function and can be used to detect urgent needs for help among persons with ADRD such as a fall. Three contact sensors can detect whether a door or cabinet is opened or closed (often placed on a front door, refrigerator, or medicine cabinet); these sensors can measure whether the person with ADRD is accessing important areas of the home and can help to determine if basic care plans are followed or activities of daily living (ADLs) are performed as expected. A toilet sensor is also mounted inside a tank that can monitor flushes. A bed occupancy sensor is placed between the mattress and box spring that can monitor time in and out of bed for the person with ADRD, as such occupancy routines can help to detect potential early stage symptoms of a number of health conditions (e.g., night time rest is frequently interrupted due to pain).

Alerts are sent to the family caregiver as well as a nurse care manager that monitors the real-time information generated by the eNeighbor sensors. An example monitoring event could occur as follows: a motion sensor detects the person with ADRD has entered a bathroom. Once the person with ADRD enters the bathroom, the motion and toilet sensors' timers are set at 10 minutes to determine whether any motion occurs in the bathroom or the toilet is wet or dry. If the motion or toilet sensors in the bathroom do not detect any activity within 10 minutes (or another household sensor detects activity in some other area of the home), an action alert is sent to notify the caregiver and nurse care manager that an expected ADL-using the bathroom-did not take place. eNeighbor sensors operate according to self-adapting thresholds (e.g., time expected to complete a given ADL) that can be set by the family caregiver or the nurse care manager upon installation of the system; if the person with ADRD is outside the normal timing threshold, the eNeighbor sensors will then alert the family caregiver and nurse care manager.

[figure not shown]
The technology platform of eNeighbor relies on wireless infrastructure that allows for remote monitoring via alerts that are communicated to the family caregiver's or nurse care manager's personal computers or handheld devices. eNeighbor also includes a private care coordination and socialization tool for the family caregiver of the person with ADRD through the MyHealthsense web portal. MyHealthsense provides scheduled reports to the family caregiver and the nurse care manager that summarizes eNeighbor sensor activity and links this information to the person with ADRD's electronic health record. In this manner, primary care providers can review the person with ADRD's daily function.

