In addition to administering informed consent forms to family caregivers and LARs, we will additionally provide HIPAA forms (either in-person or via mail and online formats) for the family caregiver and LAR to review and sign. To complete this procedure, the Family Caregiver Consent Form, the LAR Consent Form, and the HIPAA form will be utilized.

Following the securing of consent of primary caregivers and LARs, Verbal Assent of persons with ADRD will take place (see supplemental documents uploaded to IRB). While ideally this may take place simultaneously with the consent procedures above, there may be a delay in time (hopefully no more than several days) between when consent is secured from family caregivers and LARs and assent of the person with ADRD.

Baseline

As soon as possible following the completion of consent, HIPAA, and verbal assent, the baseline survey/interview will take place. The survey/interview will ask the family caregiver to complete a survey that will ask questions about the family caregiver, the person with ADRD, and the person with ADRD’s and family caregiver’s memory loss’ emotional, psychological, physical health, the caregiver’s confidence about their care situation. The survey/interview we will also ask the family caregiver about various health events that the person with ADRD may have experienced. The baseline survey can occur in-person, in the family caregiver’s home, Mayo Building at the

PROTOCOL TITLE: A Proactive Health Monitoring Intervention for Dementia Caregivers: The eNeighbor

University of Minnesota, or another location of the family caregiver's choosing. A mail survey, telephone interview, or online survey will also be arranged if that is easier for the family caregiver. If the caregiver elects to complete the online version of the survey, the survey link will be emailed to the caregiver. To complete this procedure, the Baseline eNeighbor Survey will be utilized.

Treatment/Intervention Period

Following the completion of baseline interviews, ADRD caregivers will be randomly assigned to an eNeighbor treatment condition that receives the multi-sensor, remote monitoring system or an attention control group. Randomization (participant is assigned to either the treatment or control condition) will be completed via an a priori list generated from <http://randomizer.org> by the PI. The PI will inform the ADRD caregiver of their randomization status within 2-3 days following completion of the baseline interviews.

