Cox proportional hazard survival analyses will determine whether participation in the eNeighbor treatment group results in significantly less time to nursing home admission (e.g., admission into a 24-hour nursing home facility for at least 90 days), overnight hospitalization, emergency room use, and negative health transitions (falls, wandering) when compared to persons with ADRD in the attention control group (Specific Aim 1/Hypothesis 3). The Cox proportional hazards model is defined as the product of an unknown function of time and the exponent of a linear combination of risk variables. eNeighbor treatment vs. attention control group membership will be the independent variable of interest in the test of Hypothesis 3; time to nursing home admission, overnight hospitalization, emergency room use, and occurrence of a fall or a wandering event will serve as the dependent variables. Date of randomization will serve as baseline. Additional variables will serve as covariates, including time-invariant and time-varying measurements of stress process covariates. Likelihood ratio tests and partial odds ratios will be examined in order to determine the degree to which these variables explain the observed effects of eNeighbor on time to dependent variable occurrence.

Variations in eNeighbor Use and Setting

Empirical treatment fidelity data and context of care measures that assess heterogeneity in the use of eNeighbor within the treatment condition (e.g., frequency and duration of sensor alerts and myHealthsense website use; diverse home characteristics) will be included as a series of additional Specific Aim 1 analyses. These analyses will explore the effects of variations in eNeighbor use on the outcomes hypothesized above for persons with ADRD and their family caregivers.

Specific Aim 1/Hypothesis 4

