The cost-effectiveness of the remote monitoring technology intervention will be assessed by comparing costs of implementation and healthcare utilization between persons with ADRD in the treatment condition and those in the attention control. The analysis will be conducted from the perspective of the payer (i.e., the public). Costs in the numerator of the incremental cost-effectiveness ratio (ICER) will be determined by identifying the differences in Medicare and Medicaid expenditures for persons with ADRD across the eNeighbor treatment and attention control groups using aggregated (“rolled up”) Medicare and Medicaid claims matched to the individual participant by Social Security number for the 18 months of participation. Because the differences in costs derive from a randomized trial, an evaluation of the difference in mean costs can determine significance. In addition, the direct costs of the intervention will be included as the cost of the remote sensor hardware, staff time (i.e., the Director of Nursing and Technology, who will track her hourly effort related to monitoring eNeighbor activities and assisting ADRD caregivers over a 1.5-year period), and installation costs over the 18-month study period.

The differences in effectiveness included in the denominator of the ICER will be measured using 5 ADRD caregiver and person with ADRD outcome measures: a) the standard cut-point of

“moderate or higher” burden on the Zarit Burden Interview;⁷⁷ b) the standard cut-point of “major depression” on the Center for Epidemiological Studies Depression scale;⁷⁸ c) fall (occurred or not); d) wandering event (occurred or not); e) nursing home admission (placed or not); f) hospitalization (overnight use or not); and g) emergency room use (used or not). Significant differences in cost will be investigated. Sensitivity analysis will be performed where parameter uncertainty exists. Where possible, evaluation of these ICERs will be based on comparisons in prior literature to determine the overall costs and effectiveness of eNeighbor.

Analysis: Specific Aim 2

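### Only treatment-arm caregivers get sensor alerts, and unblinded caregivers report falls and wandering, so ascertainment of these two outcomes may differ by arm

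*Combined protocol and SAP*

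**What the plan says.** **The device.** Section 4.1 says the motion sensors "can be used to detect urgent needs for help among persons with ADRD such as a fall". Contact sensors are often put on a front door, and wandering is named among the situations the alerts are meant to address. "Alerts are sent to the family caregiver as well as a nurse care manager".

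**The reporter.** In the baseline interview (Section 5.2), "we will also ask the family caregiver about various health events that the person with ADRD may have experienced". For follow-up, Section 5.3 has caregivers complete the measures every 6 months to 18 months, and states that they answer all surveys. Treatment-arm caregivers also have monthly contact with the Director of Nursing and Technology. The control-arm calls described in Section 5.3 are tied to the surveys.

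**The analyses.** Section 17.3 uses falls and wandering in three ways: as frequencies in growth curve models; in Cox models, where "occurrence of a fall or a wandering event will serve as the dependent variables"; and as yes/no effectiveness measures (c) and (d) in the cost-effectiveness ratio. Section 3.2 lists both as secondary outcomes.

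**Independent data.** The one source that does not pass through the caregiver is Medicare and Medicaid claims, "matched to the individual participant by Social Security number for the 18 months of participation". Section 17.3 plans these for the cost numerator, and Section 5.3 makes giving the number optional. Nursing home admission is defined in the text; a fall and a wandering event are not.

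**The concern.** The randomized treatment is itself an event detector, and it informs the person who later reports the outcome. An identical questionnaire in both arms cannot correct for a difference in what respondents know.

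Unequal knowledge is plausible in this population. Eligibility does not require the caregiver to live with the person with dementia, the screening text in Section 5.2 admits people who share the caring role, and the needs assessment in the same section gives living alone with little oversight as a reason for monitoring. A control caregiver in that position may never hear of an uninjured fall, while a treatment caregiver may be alerted to it.

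If so, a real reduction in falls could be masked, and a device with no effect could appear to cause falls. Without a record of how each event became known, the analyst cannot later separate awareness from effect.

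**Working it through.** **The plan's own figures.** Section 17.2 sought a sample "sufficient to detect a group difference of 0.50 standard deviation units", at a type I error of .05 and power of .80, and found 200 caregivers sufficient with 20% attrition. A simple two-group calculation gives 63 per arm, 126 in total, and 126/0.80 = 158 after attrition. So 200 is enough on that basis, although the formula does not return 200 itself; the plan cites a hierarchical method whose variance inputs it does not give. None of this bears on falls or wandering: the plan states no event rate, hazard ratio or power for Hypothesis 3. I take only the evaluable number from it: 200 × 0.80 = 160, or 80 per arm.

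**Step 1: rates and hazards.** All awareness shares are assumptions. If caregivers learn of a fixed share of events in each arm:

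observed ratio = true ratio × (treatment share / control share)

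| Control share | Treatment share | True 1.00 seen as | True 0.70 seen as |
|---|---|---|---|
| 80% | 80% | 1.00 | 0.70 |
| 80% | 90% | 1.13 | 0.79 |
| 70% | 90% | 1.29 | 0.90 |
| 60% | 90% | 1.50 | 1.05 |
| 90% | 80% | 0.89 | 0.62 |

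The last row is the opposite case, in which treated caregivers report a smaller share.

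**Step 2: effect on the Cox test.** Assume a true 18-month control probability p of at least one fall of 0.30 to 0.50, exponential times and 80 evaluable per arm. With L = −ln(1 − p):

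- expected first known events: 80 × [1 − exp(−L × control share)] in control and 80 × [1 − exp(−L × true HR × treatment share)] in treatment; their sum is D
- a = √(D/4) × ln(observed HR)
- P(significant benefit) = Φ(−a − 1.96); P(significant harm) = Φ(a − 1.96)

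Example with p = 0.30, true HR 0.70 and shares of 70% v 90%: D is about 34, the observed HR is 0.90, a = −0.31 and P(benefit) = 4.9%.

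- True HR 0.70: the chance of a significant benefit is about 18% to 28% with equal shares of 80%, and about 5% to 6% at 70% v 90%.
- True HR 1.00: the chance of a significant apparent harm rises from 2.5% to about 12% to 18% at 70% v 90%.
- True HR 1.00 in the opposite case (90% v 80%): the chance of a false significant benefit rises from 2.5% to about 6% to 7%.

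**Step 3: yes/no outcomes.** A person counts as having fallen if at least one fall is known. For someone with one fall, the 70% v 90% gap carries over in full (0.90/0.70 = 1.29). For someone with two falls and independent awareness, the shares become 1 − 0.30² = 0.91 and 1 − 0.10² = 0.99, a ratio of 1.09. ICER items (c) and (d) are therefore distorted less than the rates where events recur.

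**Step 4: would excluding alert-only events remove the bias?** Only treated caregivers can have such events. At 70% v 90%, the exclusion is unbiased only if it removes exactly the 20 points that would otherwise have been missed. If instead half of the known treatment-arm events are alert-only (assumed), 0.90 × 0.5 = 0.45 remain. A true 1.00 is then seen as 0.45/0.70 = 0.64, and a true 0.70 as 0.45. The exclusion can create a spurious benefit, so it cannot be the main analysis.

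**The case against.** A reader might infer that Hypothesis 3 event counts are inflated in the treatment arm. The documents do not support this, for five reasons.

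- No awareness rates are given. If alerts reveal real falls, treatment-arm counts are more complete and control counts fall short. Inflation proper would need false alerts to be reported as events, and the plan does not say alerts are counted as outcomes; it describes alert data for analyses of use within the treatment arm.
- The direction is not settled. Caregivers are unblinded, and the consent script in Section 22.1 tells them that the team expects benefit, which could lower reporting in the treatment arm. Section 9.1 also asks for the person most responsible for hands-on care, so a control share as low as 60% is purely an assumption.
- Hypothesis 3 also covers hospitalization and nursing home admission, and the Cox models add emergency room use. A caregiver hardly needs a sensor to know of these.
- Learning of an event earlier does not shift a Cox analysis if the date of the event itself is recorded.
- The text states detection for falls. For wandering it supports alerts and a door sensor, not stated direct detection.

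The follow-up surveys and the Disposition Form are not in the documents, so they may already define events or ask how they came to light.

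These points limit the claim in size, direction and scope. They do not remove it: the treatment informs the reporter in one arm only, and the plan describes nothing to offset that.

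**Conclusion.** The concern stands for falls and wandering only. As written, the plan allows ascertainment of these two secondary outcomes, and of ICER items (c) and (d), to differ by arm. Greater awareness in the treatment arm would push results toward no benefit or apparent harm; expectation of benefit could push the other way, so the net direction is uncertain.

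The size is illustrative because every awareness share and event rate used here is assumed. At 70% v 90% a true rate ratio of 0.70 is seen as 0.90, with equal awareness there is no bias, and yes/no measures are distorted less when events recur. The primary outcome, caregiver self-efficacy and competence, does not depend on these event counts. This is a cheap improvement to the design, and the documents do not show that any result is wrong.

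**What to change.** 1. **Record the route to knowledge.** In both arms, under one written definition of a fall and of a wandering event, record for each reported event its date and how the caregiver learned of it, ticking all that apply: saw or found, was told, system alert. This has to be collected with the event; it cannot be recovered reliably afterwards.
2. **Keep all reported events as the main analysis.** Pre-specify exclusion of alert-only events (no other route ticked) as a sensitivity analysis and report the two together as a range. State that the exclusion acts on one arm only and can favour treatment, so the range is not a formal bound. Do the same for ICER items (c) and (d).
3. **Let overnight hospitalization, emergency room use and nursing home admission lead the interpretation of Hypothesis 3.** All three are already in the Cox models. Check them against claims where a Social Security number was supplied, and report how many participants that covers. Note two limits: the claims are aggregated and may not identify falls or dates, and care-seeking may itself respond to alerts, because Section 5.2 has the Director of Nursing and Technology arrange services when alerts occur.

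The cost is one added survey item per event, one extra sensitivity analysis and some SAP wording. The downside is less emphasis on falls and wandering, which the device is meant to prevent.
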